22 February 2023

Identifiers: NCT06119113

Brief Title: Evaluation of Wound Infection Rates and Cosmetic Results of Different Suture Materials in Cesarean Skin Incision

STUDY PROTOCOL

1. Name of the study:

Evaluation of Wound Site Infection, Early and Late Wound Healing and Cosmetic Results of Vicryl (Polyglactin 910), Monocryl (Polyglecaprone 25) and Prolene (Polypropylene) Suture Materials Used in Pfannenstiel Skin Incision in Caesarean Section Surgery

2. Purpose and importance of the research (main purpose, secondary purposes):

Our primary aim with this study is to evaluate the early and late cosmetic results and patient preference of skin incision in a frequently performed surgery such as cesarean section.

Caesarean section is the most common surgery in women worldwide, and the incidence of cesarean section is increasing worldwide. 32% of pregnant women in the USA [1] and 48% in Turkey [2] give birth by cesarean section. Due to the high frequency of CS, it is essential to determine the surgical incision technique that yields the optimal cosmetic outcome of the incision scar. [4–5]. The incidence of wound complications following cesarean delivery has been reported to be between 3% and 30%; such wound complications include surgical site infection, hematoma, seroma, and wound dehiscence [6–7].

The skin is typically approximated with absorbable sutures, non-absorbable sutures, tissue adhesive or stapler after closing the abdominal layers and, if necessary, the subcutaneous fat tissue [8]. However, the suture material for optimal subcuticular skin closure is unclear, but the safest option is determined in terms of wound complications. It is important. Vicryl (Poliglactin 910), Monocryl (Poliglekapron 25) and Prolene (polypropylene) are the most commonly used suture materials for closing the skin incision.

The structure of the sutures may vary and their effects on biological healing processes may also vary [9]. Polyglactin 910 (Vicryl Rapide) is an absorbable, multifilament synthetic braided suture consisting of glycolide and L-lactide copolymer and its absorption period is 5076 days. Poliglekaprone 25 (Monocryl) is a monofilament synthetic absorbable suture made of glycolide and epsilon copolymer, its absorption period is 90-120 days. Polypropylene (prolene) monofilament is a non-absorbable synthetic suture with high tensile strength and minimal tissue reaction.

Clinical data in available studies are conflicting. In the animal studies of Sharp WV and colleagues comparing multifilament sutures with monofilament sutures, an increase in surgical site infection was found in multifilament sutures [10]. Tuuli et al. No significant difference was found in the risk of surgical site infection in patients treated with Vicryl compared with Monocryl (6.1% vs. 5.1%; P = .58). Buresch et al. In his study, he compared the wound complication rates of Monocryl (Poliglekapron 25) and Vicryl (Polyglactin 910), and closure with Monocryl was associated with a significantly reduced overall wound complication rate. (14.4% compared to 8.8%; P=0.04). Koroglu N, 2020 No statistically significant difference was observed between Vicryl (polyglactin 910) and prolene

(polypropylene) in terms of early wound complications or superficial infection. (8.3% in the polypropylene group vs 10.6% in the polyglactin 910 group, $p = .642$), but cosmetic results and patient satisfaction were not evaluated in this study. Cromi A et al. In his study, a total of 158 patients were evaluated with POSAS (Patient and Observer Scar Assessment Scale), VAS (Visual analog scale), VSS (Vancouver Scar Scale (VSS) scar evaluation scales, staple (40 patients), monocryl (45 patients), vicryl (40 patients).) and prolene (33 patients) sutures were used in 4 groups, and they determined that there was no significant difference in the cosmetic results of the wounds in the 2nd month and 6th month evaluations.

There are many scales used to evaluate the scar. The most important of these and the ones we will use in our work are; Vancouver Scar Scale (VSS) and Patient and Observer Scar Assessment Scale (POSAS) are scar assessment scales.

Vancouver Scar Scale (VSS), developed by Sullivan et al. in 1990 to evaluate scars, includes four parameters (elasticity, height, vascularity and pigmentation) and is scored between 0 and 14.

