post-op day if there is no problem after the surgery. Patients will be called for follow-up on the 10th post-operative day, 2nd month and 6th month. On the 10th post-operative day, the wound will be evaluated for infection (erythema, tenderness and purulent discharge will be considered as wound infection). If deemed appropriate, the sutures of the patients in the prolene suture group will be removed. All groups coming for follow-up will be evaluated for scar classification on the 10th day, 2nd month and 6th month post-op, first with the standardized scar evaluation scale (Sullivan T), then with the patient and observer evaluation scale (POSAS) and the Vancouver Scar Scale (VSS). and will be evaluated by the observing doctor. Additionally, patients will be categorized according to the classification recommended by the international scar management advisory panel at 2 months and 6 months.

The Patient and Observer Assessment Scale (POSAS) is a questionnaire developed to evaluate scar quality. Observer by rating scale based on clinically relevant scar characteristics consists of five patient six-item scales (Observer and Patient Scales) (Table 1) [13 , 14]. Observer ; It scores six items: vascularization, pigmentation, thickness, surface roughness, flexibility and surface area. Patient ; It scores six items: pain, itching, colour, thickness, relief and flexibility [14]. All items included are scored on a multiple 10-point scale, where 1 point is given when the scar characteristic is similar to 'normal skin' and 10 points are given when it reflects the 'worst scar'. All items are summed to determine the total scar score, with a higher score representing worse scar quality.

The Vancouver scar scale (VSS) consists of four variables: vascularization, height (thickness), elasticity and pigmentation. The total score varies between 0 and 14, with 0 points reflecting normal skin. (Table 2)

Table 1

Patient and Observer Scar Evaluation Scale (POSAS)

Observer Scar Assessment Scale (OSAS)

Normal skin 1 2 3 4 5 6 7 8 9 10 worst scar imaginable

| | | | | | | | | | | |
|---------------------|---|---|---|---|---|---|---|---|---|---|
| Vascularity | 0 | 0 | 0 | 0 | 0 | 0 | 0 | 0 | 0 | 0 |
| Pigmentation | 0 | 0 | 0 | 0 | 0 | 0 | 0 | 0 | 0 | 0 |
| Thickness | 0 | 0 | 0 | 0 | 0 | 0 | 0 | 0 | 0 | 0 |
| Relief | 0 | 0 | 0 | 0 | 0 | 0 | 0 | 0 | 0 | 0 |
| Pliability | 0 | 0 | 0 | 0 | 0 | 0 | 0 | 0 | 0 | 0 |

Patient Scar Assessment Scale (PSAS)

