No, no complaints 1 2 3 4 5 6 7 8 9 10 Yes, worst imaginable

Is the scar painful ? 0 0 0 0 0 0 0 0 0 0

| | |
|--|----------------------|
| Is the scar itching ? | 0 0 0 0 0 0 0 0 0 |
| No, as normal skin | 1 2 3 4 5 6 7 8 9 10 |
| Is the color of the scar different? | 0 0 0 0 0 0 0 0 0 0 |
| Is the scar more stiff ? | 0 0 0 0 0 0 0 0 0 0 |
| Is the thickness of the scar different ? | 0 0 0 0 0 0 0 0 0 0 |
| Is the scar irregular ? | 0 0 0 0 0 0 0 0 0 0 |

Table 2

Vancouver Scar Scale

| Scar Characteristic | Puan |
|---------------------|------|
| <hr/> | |
| Vascularity | |
| Normal | 0 |
| Pink | 1 |
| Red | 2 |
| Purple | 3 |
| <hr/> | |
| Pigmentation | |
| Normal | 0 |
| Hypopigmentation | 1 |
| Hyperpigmentation | 2 |
| <hr/> | |
| Pliability | |
| Normal | 0 |
| Supple | 1 |
| Yielding | 2 |
| Firm | 3 |

| | |
|-------------|---------------|
| Ropes | 4 |
| Contracture | 5 |
| (mm) | Height |
| Flat | 0 |
| <2 MM | 1 |
| 2-5 MM | 2 |
| >5 MM | 3 |

4. Number of patients and volunteers to be included in the research, their nature and reason for selection (age ranges, gender, etc.).

Women between the ages of 18-45 who had their first cesarean delivery in our hospital at 37 weeks and later will be included in the study.

5. Parameters to be checked (must be written one by one and clearly),

Preop:

- Age
- Gravida, parity, living child, pattern of previous births
- BMI
- Week of birth
- Caesarean section indication - Preop hemogram, htc Interop: – Operation time Postop:
- Maternal post-op 6th hour hemogram, WBC value
- Mother's hospital stay
- Post-op 10th day, 2nd month and 6th month, scar grading will be done with PSOAS and VSS. - scar length (cm)

6. Where and by whom to look at the parameters

The patients' incisions will be evaluated by the principal and assistant investigator during routine outpatient clinic checks.

7. Which of the parameters to be used in the research are routine for that disease group and which are requested specifically for the research?

Pregnant women who have undergone cesarean section will receive the follow-up and treatment we routinely do. In our clinic, Vicryl (Polyglactin 910), Monocryl (Poliglekapron 25) and Prolene (polypropylene) sutures are used, depending on the surgeon's preference and the

patient's subcutaneous tissue, for routine skin suturing. No research-specific examination will be required.

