8. Estimated working period, start and end dates, The starting date is February 22, 2023 and the anticipated working period is 6 months.

9. Criteria for inclusion in the study, exclusion from the study and withdrawal from the study,

Inclusion criteria:

- Between 18-45 years old
- >37w patients who had primary cesarean section in our hospital
- Patients with Phannenstiel incision and subcutaneous closure

Exclusion criteria:

- Women <18 years and >45 years old
- Those with a history of Keloids
- Those with suprapubic incision due to previous surgery
- Those with signs of infection at or near the incision line during cesarean section
- Known hypersensitivity to any of the suture materials used
- Having a medical disease that causes immune suppression, such as DM, chronic corticosteroid use
- Failure to obtain informed consent from the patient

10. The study will be terminated when patients meeting the inclusion criteria are reached.

11. The statistical methods that will be used in evaluating the data obtained as a result of the research should be explained.

G –Power 3 software package program was used to calculate the sample size of our study. Data from a similar study conducted by Cromi et al. were taken into account (18). For our study to be conducted in three arms, assuming Type 1 (alpha) error margin: 0.005 and Type 2 (beta) error margin: 0.20, the F value was calculated as 0.20 and the sample size was 243 cases. Considering the possibility of loss in 30% of the cases during the study period, the number of cases was planned to be at least 324.

SPSS 20 package program will be used to analyze the data obtained from our study. The Kolmogorov-Smirnov test will be applied to evaluate the distribution of continuous variables.

One-Way ANOVA and Kruskal-Wallis test will be used to compare groups in terms of parametric (homogeneous) and non-parametric (heterogeneous) continuous variables, respectively. Chi-square test will be used to compare groups for categorical variables (percentage). The change in scar evaluation criteria over time will be evaluated with the Wilcoxon matched pairs test, and the relationship between them will be evaluated with the Spearman's rho correlation test. $p < 0.05$ will be considered statistically significant.

12. Resources

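### No primary score, visit, multiplicity rule or pairwise step is stated, and the sample size names no outcome and conflicts with the analysis alpha and the stated loss

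*Combined protocol and SAP*

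**What the plan says.** - **Aim.** Section 2 says: "Our primary aim with this study is to evaluate the early and late cosmetic results and patient preference of skin incision". Section 3 (expected benefits and risks) adds the safest closure and fewer wound complications, without ranking them against the cosmetic aim.
- **Scores and visits.** Section 5 says: "Post-op 10th day, 2nd month and 6th month, scar grading will be done with PSOAS and VSS". Section 4 (type, scope and design) adds that "patients will be categorized according to the classification recommended by the international scar management advisory panel at 2 months and 6 months", and has infection assessed at day 10. Nothing is marked as primary.
- **Analysis.** In Section 11, "One-Way ANOVA and Kruskal-Wallis test will be used to compare groups", with chi-square for categorical variables. Also, "The change in scar evaluation criteria over time will be evaluated with the Wilcoxon matched pairs test"; that test compares visits within a woman, not sutures. Spearman correlation completes the list. One threshold, 0.05, applies to everything.
- **Sample size.** Section 11 uses "Type 1 (alpha) error margin: 0.005 and Type 2 (beta) error margin: 0.20, the F value was calculated as 0.20", giving 243 cases, with an earlier trial of skin closure methods as the source. It then allows for "possibility of loss in 30% of the cases during the study period, the number of cases was planned to be at least 324".

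**The concern.** The study asks which of three sutures gives the best scar, and the plan leaves two decisions open until the data are seen.

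The first is which result counts. With two scales, three visits and no ranking, a cosmetic claim can rest on whichever combination falls below 0.05.

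The second is which suture differs. A significant ANOVA or Kruskal-Wallis test says only that the three groups are not all alike. The analyst would have to add pairwise tests afterwards, without a rule.

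The sample size does not settle either question, because it identifies no outcome. Its alpha, power, effect size, N and loss allowance also cannot all be true together.

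**Working it through.** **Inputs.** From Section 11: alpha 0.005 (design) and 0.05 (analysis), beta 0.20, effect size 0.20 (read as Cohen's f), N = 243, loss 30%, planned enrolment 324. Three arms are from Section 4. Equal arms are assumed; the plan gives no ratio and allocates by surgeon preference.

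**1. The plan's N = 243.** Power of a one-way ANOVA comes from the noncentral F distribution with 2 and N − 3 degrees of freedom and noncentrality λ = f² × N.
- At N = 243, λ = 0.04 × 243 = 9.72.
- Alpha 0.05: critical F = 3.03, power 79.8%. Reaching 80% in equal arms needs 246, so 243 is reproduced to within about 1%.
- Alpha 0.005: critical F = 5.42, power 49.5%. Reaching 80% in equal arms needs 399.

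So 243 fits 0.05 and does not fit the printed 0.005.

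**2. The plan's 324.**
- 243 / (1 − 0.30) = 347.1, so 348.
- 243 × 1.30 = 315.9, so 316.
- 243 / (1 − 0.25) = 324 exactly.
- 324 × 0.70 = 226.8, about 227 evaluable: λ = 9.08, power 76.9% at 0.05 (45.5% only if 0.005 is meant).

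**3. False positives without a primary.** The plan lists no tests, so the count is an assumption: POSAS total and VSS at three visits make 2 × 3 = 6 three-group tests at 0.05.
- Independent tests: 1 − 0.95⁶ = 26.5%.
- Simulation with equal correlation between all six scores (arms of 76, 76 and 75, no true differences): 24.5% at correlation 0.3, 21.2% at 0.5, 17.2% at 0.7 and 11.0% at 0.9.

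The documents give no correlation, so the answer is the range 11% to 26.5%. Repeated scoring of one scar on overlapping items makes the low correlations less plausible. In the other direction, testing the observer and patient parts of POSAS separately would make nine tests (1 − 0.95⁹ = 37% if independent).

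**4. Pairwise step.** With no true differences, three unprotected pairwise tests on one score give a 12.2% chance of a false claim. Running them only after a significant three-group test brings this to 5.0%. When one arm truly differs, a false claim on the equal pair occurs 4.7% to 5.0% of the time.

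**5. Power of that step at f = 0.20, alpha 0.05, equal arms.** Evenly spaced means give a largest standardized difference of 0.20 × √6 = 0.49. One differing arm gives 0.20 × 3/√2 = 0.42.

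| Evaluable | One arm differs (0.42) | Evenly spaced, largest pair (0.49) | Evenly spaced, each other pair |
|---|---|---|---|
| 243 (81 per arm) | 72% | 79% | about 33% |
| 227 (76/76/75) | 68% | 76% | about 31% |

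**6. Scale ranges.** POSAS has five observer items in Section 2 and Table 1, but six in one sentence of Section 4. With six patient items, the total runs from 11 to 110 or from 12 to 120. VSS is stated as 0 to 14, but the Table 2 maxima sum to 3 + 2 + 5 + 3 = 13.

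**The case against.** Several stronger readings are tempting, and the documents do not support them.

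- **The study has only about 50% power.** A reader might infer this from the printed 0.005. But 243 fits 0.05, the analysis uses 0.05, and 0.005 is probably a misprint. The 49.5% applies only if 0.005 is really meant. At 0.05 the shortfalls are small: 79.8% with 243 and 76.9% with 227. A tenfold correction (0.05/10) would also give 0.005, but the plan does not say so and 243 does not fit it.
- **The sample size has no outcome behind it.** It cites a trial that, according to Section 2, used POSAS, VAS and VSS at months 2 and 6. The gap is narrower: the plan does not say which score or visit gave f = 0.20, and quotes no mean or standard deviation. Whether that trial supports 0.20 cannot be checked from these documents.
- **The error rate is 26.5%.** That is the independent end of a range, on an assumed count of six.
- **The scale discrepancies prevent a primary from being chosen.** They do not. The six-item sentence is the outlier for POSAS, and VSS can be scored from the Table 2 rows. They only need to be put right.

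It can also be said that confounding by surgeon preference threatens a suture claim more than chance error does. That may be so, and nothing here removes it. It does not excuse the gap: the plan states a primary aim, a power calculation and a significance threshold, so it is not purely descriptive.

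**Conclusion.** The point holds, as something that should be corrected. No primary score or visit is named, no rule limits the number of chances at 0.05, and no step compares one suture with another. On the assumed six tests, the false-positive chance is two to five times the nominal 5%.

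The sample size paragraph is inconsistent as written: alpha 0.005 does not give 243, and a 30% loss does not give 324. Read at 0.05, the planned power is close to 80% before loss and about 77% after the stated loss. The defect is therefore mainly one of specification and consistency, not a badly undersized study.

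These figures assume that 0.20 is Cohen's f and that arms are equal. Unequal arms, which surgeon preference makes likely, would lower the power of some comparisons.

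**What to change.** 1. Name one primary score and one visit, and say that f = 0.20 refers to it. Label the other scores and visits, the scar classification and infection as secondary or descriptive.
2. State one alpha in both places (243 fits 0.05). Restate the power as about 80% with 243 evaluable and about 77% with 227 after 30% loss, or state the loss as 25%.
3. Test the primary once with the three-group test at 0.05. Run the three pairwise comparisons at 0.05 only if it is significant, using Mann-Whitney pairs if Kruskal-Wallis is used.
4. When fixing the primary score, reconcile the POSAS observer item count (five or six) and the VSS range (14 or 13).

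**Cost.** These are changes of wording. Enrolment changes only if the sponsor wants 243 evaluable after a 30% loss, which needs 348. Results outside the primary will carry less weight. Pairwise power must be reported as below 80%: 72–79% for the largest difference with 243 in equal arms, 68–76% with 227, and lower for smaller contrasts or unequal arms. Requiring the three-group test first limits chance error only; it does nothing about confounding by surgeon choice.

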post-op day if there is no problem after the surgery. Patients will be called for follow-up on the 10th post-operative day, 2nd month and 6th month. On the 10th post-operative day, the wound will be evaluated for infection (erythema, tenderness and purulent discharge will be considered as wound infection). If deemed appropriate, the sutures of the patients in the prolene suture group will be removed. All groups coming for follow-up will be evaluated for scar classification on the 10th day, 2nd month and 6th month post-op, first with the standardized scar evaluation scale (Sullivan T), then with the patient and observer evaluation scale (POSAS) and the Vancouver Scar Scale (VSS). and will be evaluated by the observing doctor. Additionally, patients will be categorized according to the classification recommended by the international scar management advisory panel at 2 months and 6 months.

The Patient and Observer Assessment Scale (POSAS) is a questionnaire developed to evaluate scar quality. Observer by rating scale based on clinically relevant scar characteristics consists of five patient six-item scales (Observer and Patient Scales) (Table 1) [13 , 14]. Observer ; It scores six items: vascularization, pigmentation, thickness, surface roughness, flexibility and surface area. Patient ; It scores six items: pain, itching, colour, thickness, relief and flexibility [14]. All items included are scored on a multiple 10-point scale, where 1 point is given when the scar characteristic is similar to 'normal skin' and 10 points are given when it reflects the 'worst scar'. All items are summed to determine the total scar score, with a higher score representing worse scar quality.

The Vancouver scar scale (VSS) consists of four variables: vascularization, height (thickness), elasticity and pigmentation. The total score varies between 0 and 14, with 0 points reflecting normal skin. (Table 2)

Table 1

Patient and Observer Scar Evaluation Scale (POSAS)

Observer Scar Assessment Scale (OSAS)

Normal skin 1 2 3 4 5 6 7 8 9 10 worst scar imaginable

| | | | | | | | | | | |
|---------------------|---|---|---|---|---|---|---|---|---|---|
| Vascularity | 0 | 0 | 0 | 0 | 0 | 0 | 0 | 0 | 0 | 0 |
| Pigmentation | 0 | 0 | 0 | 0 | 0 | 0 | 0 | 0 | 0 | 0 |
| Thickness | 0 | 0 | 0 | 0 | 0 | 0 | 0 | 0 | 0 | 0 |
| Relief | 0 | 0 | 0 | 0 | 0 | 0 | 0 | 0 | 0 | 0 |
| Pliability | 0 | 0 | 0 | 0 | 0 | 0 | 0 | 0 | 0 | 0 |

Patient Scar Assessment Scale (PSAS)

No, no complaints 1 2 3 4 5 6 7 8 9 10 Yes, worst imaginable

Is the scar painful ? 0 0 0 0 0 0 0 0 0 0

| | |
|--|----------------------|
| Is the scar itching ? | 0 0 0 0 0 0 0 0 0 |
| No, as normal skin | 1 2 3 4 5 6 7 8 9 10 |
| Is the color of the scar different? | 0 0 0 0 0 0 0 0 0 0 |
| Is the scar more stiff ? | 0 0 0 0 0 0 0 0 0 0 |
| Is the thickness of the scar different ? | 0 0 0 0 0 0 0 0 0 0 |
| Is the scar irregular ? | 0 0 0 0 0 0 0 0 0 0 |

Table 2

Vancouver Scar Scale

| Scar Characteristic | Puan |
|---------------------|------|
| <hr/> | |
| Vascularity | |
| Normal | 0 |
| Pink | 1 |
| Red | 2 |
| Purple | 3 |
| <hr/> | |
| Pigmentation | |
| Normal | 0 |
| Hypopigmentation | 1 |
| Hyperpigmentation | 2 |
| <hr/> | |
| Pliability | |
| Normal | 0 |
| Supple | 1 |
| Yielding | 2 |
| Firm | 3 |

| | |
|-------------|---------------|
| Ropes | 4 |
| Contracture | 5 |
| (mm) | Height |
| Flat | 0 |
| <2 MM | 1 |
| 2-5 MM | 2 |
| >5 MM | 3 |

4. Number of patients and volunteers to be included in the research, their nature and reason for selection (age ranges, gender, etc.).

Women between the ages of 18-45 who had their first cesarean delivery in our hospital at 37 weeks and later will be included in the study.

5. Parameters to be checked (must be written one by one and clearly),

Preop:

- Age
- Gravida, parity, living child, pattern of previous births
- BMI
- Week of birth
- Caesarean section indication - Preop hemogram, htc Interop: – Operation time Postop:
- Maternal post-op 6th hour hemogram, WBC value
- Mother's hospital stay
- Post-op 10th day, 2nd month and 6th month, scar grading will be done with PSOAS and VSS. - scar length (cm)

6. Where and by whom to look at the parameters

The patients' incisions will be evaluated by the principal and assistant investigator during routine outpatient clinic checks.

7. Which of the parameters to be used in the research are routine for that disease group and which are requested specifically for the research?

Pregnant women who have undergone cesarean section will receive the follow-up and treatment we routinely do. In our clinic, Vicryl (Polyglactin 910), Monocryl (Poliglekapron 25) and Prolene (polypropylene) sutures are used, depending on the surgeon's preference and the

patient's subcutaneous tissue, for routine skin suturing. No research-specific examination will be required.

8. Estimated working period, start and end dates, The starting date is February 22, 2023 and the anticipated working period is 6 months.

9. Criteria for inclusion in the study, exclusion from the study and withdrawal from the study,

Inclusion criteria:

- Between 18-45 years old
- >37w patients who had primary cesarean section in our hospital
- Patients with Phannenstiel incision and subcutaneous closure

Exclusion criteria:

- Women <18 years and >45 years old
- Those with a history of Keloids
- Those with suprapubic incision due to previous surgery
- Those with signs of infection at or near the incision line during cesarean section
- Known hypersensitivity to any of the suture materials used
- Having a medical disease that causes immune suppression, such as DM, chronic corticosteroid use
- Failure to obtain informed consent from the patient

10. The study will be terminated when patients meeting the inclusion criteria are reached.

11. The statistical methods that will be used in evaluating the data obtained as a result of the research should be explained.

G –Power 3 software package program was used to calculate the sample size of our study. Data from a similar study conducted by Cromi et al. were taken into account (18). For our study to be conducted in three arms, assuming Type 1 (alpha) error margin: 0.005 and Type 2 (beta) error margin: 0.20, the F value was calculated as 0.20 and the sample size was 243 cases. Considering the possibility of loss in 30% of the cases during the study period, the number of cases was planned to be at least 324.

SPSS 20 package program will be used to analyze the data obtained from our study. The Kolmogorov-Smirnov test will be applied to evaluate the distribution of continuous variables.

One-Way ANOVA and Kruskal-Wallis test will be used to compare groups in terms of parametric (homogeneous) and non-parametric (heterogeneous) continuous variables, respectively. Chi-square test will be used to compare groups for categorical variables (percentage). The change in scar evaluation criteria over time will be evaluated with the Wilcoxon matched pairs test, and the relationship between them will be evaluated with the Spearman's rho correlation test. $p < 0.05$ will be considered statistically significant.

12. Resources

